The PI for this study is on faculty in the MGH Division of General Internal Medicine and is a staff physician at MGH Revere. The proposed trial will be funded by the PI's Career Development (K23) Award from the National Institute on Drug Abuse at the National Institutes of Health, and by a grant to the PI from the MGH Executive Committee on Research Claflin Distinguished Scholars Award.

II. Specific Aim

Research Aim 1: To test, in a 4 arm pilot randomized controlled trial ($N=50/group$), the effect of delivering behavioral smoking cessation content by text message and mailed nicotine replacement therapy on self-reported quit attempts (intentional non-smoking for ≥ 24 hours), pharmacotherapy adherence, and smoking abstinence at the end of treatment.

Hypothesis 1: A 12 week text messaging intervention (up to 30 days pre-quit through 8 weeks post-quit) providing behavioral support will increase the proportion of smokers making a quit attempt compared to smokers receiving no text messaging.

Hypothesis 2: A 12 week text messaging intervention will increase adherence to NRT compared to subjects receiving only 2 weeks of NRT as measured by: (a) duration of NRT use in days and (b) total mg of NRT used.

[figure not shown]
Hypothesis 3: A 12 week text messaging intervention will increase the rate of *biochemically confirmed* past 7-day point prevalent tobacco abstinence at end of treatment compared to subjects receiving no text messaging intervention.

Hypothesis 4: A 12 week text messaging intervention will increase the number of days not smoking compared to subjects receiving no text messaging intervention.

Hypothesis 5: A 12 week text messaging intervention will decrease the number of cigarettes smoked compared to subjects receiving no text messaging intervention

Study Design

Figure. Pilot randomized controlled trial schema

III. SUBJECT SELECTION

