Finally, the text messaging program will be tailored to the individual and MGH. Text messages will include the telephone number for the MGH tobacco cessation counseling services LivingTobacco-Free which accept self-referrals as well as the number for the Massachusetts state quitline.

Smokers receiving the intervention will be sent from 0 and 5 text messages per day. This is the message volume used by most smoking cessation text messaging programs.⁶⁰ Smokers are asked to enter a quit date in the first 30 days after enrollment. Those without a quit date will be sent the practice quit attempt messages. At the end of the practice quit attempt messages subjects will be asked again if they have a quit date in the next 30 days. For those who are ready to quit at time of enrollment, or those who become ready to quit after the practice attempt, up to 5 messages per day are delivered in the 2 weeks leading up to the self-designated quit

date and the 2 weeks after the quit date when they are at greatest risk for relapse.⁶¹ Messages then decrease to 3 messages per week for 8 weeks after the attempt.

b. Drugs used

Subjects randomized to the NRT or TM + NRT arms will be offered nicotine replacement therapy dependent on their smoking patterns and readiness to quit.

Daily smokers planning to quit in the next 30 days will be offered combination nicotine replacement therapy including nicotine patches and nicotine lozenges. Daily smokers will be offered nicotine patches (14 or 21 mg patches) and lozenges (2 or 4 mg lozenges). Smokers who smoke ≥ 10 cigarettes per day will be offered 21 mg patches, those who smoke < 10 cigarettes per day will be offered 14 mg patches. Daily smokers who smoke within 30 minutes of awakening will be also offered the 4 mg lozenges. Daily smokers who smoke > 30 minutes of awakening will be offered 2 mg lozenges. Daily smokers with a prior reaction to adhesives from bandaids or the nicotine patch will be offered lozenges only.

Smokers not planning to quit will be offered one box of lozenges (72 count box of 4 mg or 2 mg lozenges based on time to first cigarette as above per package instructions) to use when they are not smoking during their practice quit attempt⁵³.

The efficacy and safety of mailing nicotine replacement therapy to general population has recently been demonstrated⁵⁵.

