NRT prescriptions will be entered into the EHR and signed by the study PI ([name]), printed and faxed to the MGH Outpatient pharmacy. The MGH Outpatient pharmacy will send the NRT by mail to the subject.

NRT will be distributed in a two-week allotment. The RC will screen participants for any self-reported contraindications to NRT use or other exclusion criteria before enrollment. High-risk comorbidities (e.g. cardiovascular disease, uncontrolled hypertension) will also be assessed but will not be grounds for withholding NRT since the risks of continued smoking outweigh the potential risks of using NRT in these conditions. After verbal consent, the PI will screen medical records of subjects randomized to NRT for contraindications or exclusion criteria prior to randomization. Participants will be instructed not to use the patch or lozenges while smoking, but rather to commence use when/if they make a quit attempt or practice quit attempt (lozenges only). The most common side effect of transdermal NRT is skin irritation. Other possible but rare side effects of all forms of NRT include cardiovascular (chest pain, hypertension, tachycardia, palpitations), metabolic (hot flashes, sweats), gastrointestinal (diarrhea, dyspepsia, nausea/vomiting, flatulence/gas, hiccups), musculoskeletal (arthralgia, myalgia), neurologic (headaches, dizziness), ophthalmic (lacrimation, nystagmus), respiratory (coughing), oropharyngeal (dry mouth, alteration of taste) and psychiatric (sleep disturbance, vivid dreams) manifestations.⁶² The most common side effects of nicotine lozenges include mouth irritation or ulcers, nausea, vomiting, hiccups, abdominal pain, diarrhea, headaches and palpitations. Randomized trials of combination nicotine replacement therapy have shown increased report of adverse events but not more serious adverse events or study withdrawal among subjects receiving combination therapy compared with subjects receiving NRT monotherapy. The risk of nicotine toxicity is rare in clinical trials. Among trial subjects who achieve higher cotinine levels with nicotine therapy than with smoking alone, the most common symptoms reported were nausea, vomiting, palpitations, dizziness, and headaches and all occurred in 0.5% or fewer trial subjects.⁶³

All study subjects will be asked about adverse reactions to the nicotine patch or lozenge at weeks 1, 2 and 6.

c. Devices

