We will attempt to obtain exhaled carbon monoxide samples from study participants who self-report 7 day point prevalent abstinence at end of treatment using the coVita | Bedfont Micro+ Smokerlyzer carbon monoxide monitor. The device will be used, maintained, and calibrated in accordance with the manufacturer's instructions.

Subjects randomized to the TM and TM + NRT arms will have their mobile telephone number, first name and PCP's name entered into the MobileCommons web-based text messaging platform. Their name will be used to personalize text messages.

d. Study visits and parameters to be measured

This study will be primarily conducted by telephone contact, email if the participant chooses, and mailings with a single in-person contact for subjects reporting abstinence from smoking at the end of treatment to collect an exhaled carbon monoxide sample to confirm abstinence. Subjects will be contacted by telephone and data collected by self-report at time of enrollment (baseline assessment interview), and by telephone or email for 1, 2, and 6 weeks after enrollment (follow-up outcome assessments), and end of treatment (primary outcome).

We will also offer a qualitative exit interview to be completed by phone for 10 participants per intervention arm (TM, TM+NRT, and NRT).

Baseline assessment:

Variables obtained from the EHR:

- Demographic factors: age, sex, health insurance (commercial, Medicare, Medicaid, no insurance or other), name, and address
- Medical history: coronary heart disease, COPD, diabetes, hypertension, cancer
- Practice characteristics: PCP, practice, number of visits to practice in past year

Variables obtained from baseline telephone interview:

- Smoking patterns: daily or non-daily, years smoked, Fagerstrom test for nicotine dependence (includes time to first cigarette after waking and cigarettes smoked per day)⁶⁴, number of previous quit attempts defined as any serious quit attempt lasting ≥ 24 hours ⁶⁵ ever and in the last 12 months, during the past 30 days, on how many days did you have at least one cigarette, and do you ever use menthol cigarettes.
- Demographic factors: ethnicity, race (white, black, Native American, Asian, Native Hawaiian or other Pacific Islander, other, unknown), and education
- Any prior use of smoking cessation medication (nicotine patch, lozenge, gum, inhaler or nasal spray, varenicline, or bupropion)

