- Any prior use of behavioral treatment for smoking cessation (clinic or class, in-person counseling, telephone counseling, text messaging, alternative therapy, self help materials, or online communities and applications)
- Past month use of other tobacco products-cigars, cigarillos, smokeless tobacco, hookah, or e-cigarette

Motivation to quit, confidence to quit, and perceived 2-week distress measured using single-item instruments with 11-item likert scale

- Readiness to quit⁶⁶
- Measures of psychosocial mechanisms targeted by the text messaging
- PHQ-2 and GAD-2 screening for depression and anxiety
- Single item alcohol⁶⁷ and substance use disorder⁶⁸ screening questions and past month illegal use of drugs⁶⁹
- On an average day, about how many text messages do you send and receive on your cell phone?
- Cell phone carrier, type (smartphone) and plan details (pay per text or unlimited text messaging).
- Email for subjects that want the follow up surveys emailed
- Social security number for payment purposes

Outcome assessments:

Medication use outcomes will be assessed by telephone interview at week 1 and 2 by a second research coordinator blinded to treatment assignment: number of days patch was used in the last week and number of lozenges used each of the last two days. These will be used to calculate total duration of medication.⁷⁰.

1 & 2 week telephone outcome assessments

- Have you used nicotine patch in the past 7 days?
 - How many days in the past week did you use a nicotine patch?
- Have you used nicotine lozenges in the past 7 days?
 - How many days in the past 7 days did you use a nicotine lozenge?
 - On days when you use lozenge, how many do you use on average?
- Since starting the study, have you stopped smoking cigarettes for 1 day or longer because you were trying to quit smoking?
 - If yes→On how many of the past 7 days did you have at least one cigarette?
If 0→Have you smoked cigarettes, even a puff in the past 7 days?
- Have you experienced any side effects in the last 7 days from quit smoking medications?
- Receipt of text messages since last assessment.
- *Only Week 2*→ Would you like more nicotine medication? A refill request would be sent to your PCP and it will be billed through your regular insurance.

6 week telephone outcome assessments

- Have you used nicotine patch in the past 7 days?
 - How many days in the past week did you use a nicotine patch?
- Have you used nicotine lozenges in the past 7 days?

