The sample of smokers enrolled in the study will be characterized on baseline measures from the EHR and compared to the population of smokers whom we attempted to contact in order to determine the sample's representativeness to the target population. Variables include demographics, medical history, and practice characteristics. We will also compare baseline characteristics collected from the EHR and from baseline interviews between the 4 randomized groups to determine the success of randomization. The primary outcome analysis will be conducted as intention-to-treat, comparing the primary outcome using chi-square analysis or multiple logistic regression analysis if any baseline factor is significantly imbalanced by group ($p<0.05$) as independent variables. The 4 arm design allows for analysis as a factorial design. We will first test for interaction between the NRT and TM interventions and if no interaction is detected we will test the effect of text messaging using both TM and TM+NRT arms compared to BA and NRT arms. If interaction is present, we will compare the TM arm to BA for our primary analysis. We will secondarily compare the groups in terms of self reported 7 day PPA, biochemically confirmed abstinence, number of days not smoked, use of ≥ 1 evidence based treatments, and cigarettes per day using chi-square or t-tests or logistic or linear regression if groups are imbalanced. We will also compare the TM+NRT group with the NRT group in terms of total days of medication used and total mg of medication used over 2 weeks using linear regression. We will conduct stratified analyses of the primary outcome, 7 day PPA, treatment use and days not smoked by readiness to quit in the next 30 days.

Sample size

Hypothesis 1: A 12 week text messaging intervention (up to 30 days pre-quit through 8 weeks post-quit) providing behavioral support will increase the proportion of smokers making a quit attempt compared to a control group receiving brief advice.

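### Hypothesis 2 is about total NRT use, but the analysis counts only about days 1–14 after enrollment, and NRT may be started later than that

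*Combined protocol and SAP*

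**What the plan says.** **Hypothesis.** Section II, Hypothesis 2, measures adherence as "a) duration of NRT use in days and (b) total mg of NRT used". No time window is attached.

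**Analysis.** Section VI (Data analysis) compares TM+NRT with NRT on "total days of medication used and total mg of medication used over 2 weeks using linear regression".

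**Measurement.** Section V.d: "Medication use outcomes will be assessed by telephone interview at week 1 and 2 by a second research coordinator". Each contact asks about the past 7 days, and of these answers the section says "These will be used to calculate total duration of medication". The contacts are timed from enrollment: "by telephone or email for 1, 2, and 6 weeks after enrollment (follow-up outcome assessments". Week 6 again asks about the past 7 days. The week-12 list covers NRT among treatments used in the past 12 weeks, with no days or mg.

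**Start of use.** The pharmacy mails the supply after randomization (IV.c). Section V.b: "Participants will be instructed not to use the patch or lozenges while smoking, but rather to commence use when/if they make a quit attempt", or a practice quit attempt (lozenges only). Ready participants are those planning to quit within 30 days (III.a). In the texting program, "Smokers are asked to enter a quit date in the first 30 days after enrollment" (V.a), and "up to 5 messages per day are delivered in the 2 weeks leading up to the self-designated quit" date.

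**The concern.** The clock for counting NRT starts at enrollment. The clock for using NRT starts at an attempt that may come weeks later. No section ties the two weeks to the quit date or to first use, so use after about day 14 drops out of the Hypothesis 2 comparison even when the participant did exactly what was asked.

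Testing the effect of texting on medication use is a stated reason for having four arms (IV.c). If the counted quantity depends on when people start, an effect on timing and an effect on adherence cannot be told apart. A small or null result would then say little about adherence.

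**Working it through.** **1. What the window covers.** Past 7 days at week 1 plus past 7 days at week 2 gives nominal days 1–14. Adding week 6 (about days 36–42), the item lists ask days of use for 7 + 7 + 7 = 21 of 84 days. Days 15–35 have no such question. The week-12 item has neither days nor mg, so total use cannot be rebuilt from what is listed. The Data Collection sheets cited in section VI are not in the documents and could contain more.

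**2. What a late starter scores.** For start day s and U consecutive days of use, counted days = max(0, min(U, 14 − s)). With the planned 9 versus 12 days:

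| Start day | NRT (U = 9) | TM+NRT (U = 12) | Difference |
|---|---|---|---|
| 0–2 | 9 | 12 | 3 |
| 3 | 9 | 11 | 2 |
| 5 | 9 | 9 | 0 |
| 7 | 7 | 7 | 0 |
| 14 or later | 0 | 0 | 0 |

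A mean of 12 counted days, with all starts inside the window, needs a mean start no later than day 14 − 12 = 2, mailing included, and no missed days.

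**3. Share of a full 14-day course inside the window.**
- All start on day 3: 11/14 = 79%.
- Starts uniform over days 0–7: 1 − 3.5/14 = 75%.
- Uniform over 0–14: 1 − 7/14 = 50%.
- Uniform over 0–30: (14²/2)/30 = 98/30 = 3.27 days, and 3.27/14 = 23%; 16/30 = 53% of starters count 0.

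**4. The plan's power figure.** Section VI (Sample size) states 80% power for 9 versus 12 days, with no SD and no window, so the figure cannot be reproduced directly. The SD it implies can be solved for. With 50 × 0.75 = 37.5 per arm and two-sided 0.05 (assumed for Hypothesis 2), the normal approximation gives SD = 3 / [(1.960 + 0.842) × √(2/37.5)] = 4.64 days. The noncentral t gives 4.54 at 37 and 4.61 at 38 per arm.

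**5. Power with delayed starts.** Simulated, 37 per arm, true means 9 and 12 days. The start times and use patterns are assumptions.

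| Use pattern | No delay | All day 3 | 0–7 | 0–14 | 0–30 |
|---|---|---|---|---|---|
| A. Consecutive days, beta on 0–14, SD 4.54 in both arms | 80% | 43% | 38% | 12% | 7% |
| B. As A, use spread evenly over 14 days from start | 80% | 80% | 71% | 35% | 12% |
| C. Consecutive, normal with SD 4.54, cut at 0 and at the window | 77% | 69% | 59% | 17% | 7% |
| D. As A, but SD 3 in the mean-12 arm | 91% | 85% | 75% | 26% | 9% |

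Pattern A is extreme. With mean 12 on a 0–14 scale the largest possible SD is √(12 × 2) = 4.90, so SD 4.54 forces a nearly all-or-none shape: Beta(0.141, 0.023), with 81% above 13 days and 10% below 1 day. The low figures for early starts (43%, 38%) come from that shape; D shows what happens without it.

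**The case against.** **The two weeks are deliberate.** The mailed supply is a two-week allotment, the planning mean of 9 days is based on that offer, a refill is offered at week 2, and section VI states the window openly. This stands as a reason to keep a days 1–14 outcome. It matches how much was mailed, not when it is used, and Hypothesis 2 and section V.d both speak of total or unrestricted use.

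**Later use is not ignored.** The week-12 item feeds the section VI comparison of use of at least one evidence-based treatment. True, but that analysis carries no days or mg.

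**The window is only nominal.** Up to 10 contact attempts and the email option mean that the past-7-day periods can slip later. True; the plan does not say how slippage is handled.

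**Most may start early.** Possible, and the loss would then be small. The listed items record no date of first use, so it could not be shown afterwards. The wide start-time distributions in the table have no support in the documents either. The share-of-course figures also fit poorly for not-ready participants, who get one box of lozenges for practice attempts.

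**Texting delays quitting, so the comparison is biased against it.** A reader might infer this from the pre-quit messages, since someone receiving the full two-week block before the quit date starts NRT at about day 14. The documents do not support a direction. Only the texting program asks by message for a quit date, but IV.c also refers to participants with a quit date in both NRT arms, and texting might bring attempts forward.

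**Conclusion.** The mismatch is in the text and needs no assumption: the hypothesis is about total use, the comparison covers nominal days 1–14 from enrollment, and NRT starts at an attempt that may come after that. II (Hypothesis 2), V.b, V.d and VI must be reconciled.

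The days 1–14 comparison is not invalid. Both arms are counted over the same period from randomization, so it estimates an effect on early use: starting, and persisting to about day 14. It does not estimate the total use that Hypothesis 2 names, and a null could not be read as no effect on adherence.

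The size is unknown. A reader might take 7% or 12% as the real power for Hypothesis 2; the documents do not support that, because they give neither start times nor an SD. With all starts on day 3, power runs from about 43% to 85% across the four patterns tried. If many start after the second week, little of the difference can appear under any of them.

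Stakes are limited: this is a secondary outcome of a pilot, and the primary outcome is unaffected. It should be fixed because the fix is cheap.

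**What to change.** 1. At the existing week-2, 6 and 12 contacts, add the date of first NRT use and the days (and lozenges per day) used since the last contact. Record mailed supply separately from refills.
2. Label the days 1–14 measure as early NRT use. Beside it, report cumulative days and mg from randomization to week 12 as the measure that matches Hypothesis 2 as worded. Score reported non-use as 0; treat missed contacts as missing, not 0.
3. Report use in the 14 days from first use as supportive only, because its starting point is a post-randomization event that texting may shift.
4. Include the readiness stratum in the linear model. This is for precision; leaving it out causes no bias.
5. State the SD and the window behind the 80% power (about 4.5–4.6 days is implied at 37–38 per arm).

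The cost is a few items on contacts already scheduled and a short paragraph in section VI. No NRT instruction changes.

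There are three downsides. Recall lengthens from 7 days to about 4 weeks at week 6 and 6 weeks at week 12, and is weakest for lozenge mg. The SD may grow once refills count: at 37 per arm, power for a 3-day difference is 80% at SD 4.54, 56% at SD 6 and 36% at SD 8. Cumulative use also still reflects quit timing, relapse and refills as well as adherence, so it should not be presented as isolating adherence.

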Rationale: In order to test the effect of text messaging on medication adherence, we need to have treatment groups receiving medication and medication plus text messaging. To deliver medication, mailed NRT, like text messaging, reaches patients outside of the busy office visit. Mailed NRT alone has also been shown to increase cessation⁵⁵ and may itself be an effective intervention compared to standard care.

3. Text messaging (TM): Brief advice + 12 week personalized, tailored text messaging program.

Rationale: Text messaging shows promise as an intervention to help smokers to quit.^{8,56} However, it has not been well tested among primary care patients. Text messaging may connect those primary care smokers who do not access currently available treatment services like telephone counseling or prescribed medication with assistance outside of the clinic office.

4. Text messaging and nicotine replacement therapy (TM+NRT): Brief advice + 12 week personalized, tailored text messaging program + 2 weeks of nicotine patches and/or lozenges mailed to subject.

Rationale: As above, in order to test the effect of text messaging on medication adherence, we need to have treatment groups receiving medication and medication plus text messaging. Text messaging has been shown to increase medication adherence in other conditions³⁴⁻³⁷ and medication adherence is suboptimal among users of smoking cessation medications.^{38,39,41} Integrating text messaging within healthcare systems offers opportunities to coordinate with pharmacotherapy and this 4 group design allows us to test the effect of text messaging alone on smoking outcomes and the effect of text messaging on NRT use.

We will use stratified block randomization. We will stratify by practice and readiness to quit in the next 30 days. We will use variable block sizes. Subjects will be randomized 1:1:1:1.

After verbal consent and chart review by the PCP. Randomized enrollees will be asked to complete a baseline telephone survey. After completion of the baseline survey, participants will be mailed a \$20 gift card.

Following the telephone survey, smokers randomized to the text messaging arms (TM and TM+NRT) will have their mobile numbers, and first names entered into the MobileCommons web-based platform. The program will be tailored to readiness to quit and user-entered quit date and personalized with individual's first name.

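### The total-mg NRT regression names no covariate for baseline-determined supply: the comparison is unbiased but less precise than it could be

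*Combined protocol and SAP*

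**What the plan says.** Hypothesis 2 (Section II) measures NRT adherence by "a) duration of NRT use in days and (b) total mg of NRT used". Section VI, Data analysis, compares the TM+NRT and NRT groups on "total days of medication used and total mg of medication used over 2 weeks using linear regression". No covariate is named for this model. Elsewhere in that paragraph, adjustment is triggered only by observed baseline imbalance.

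Section V.b (Drugs used) sets what each participant is offered:
- Readiness: "Smokers not planning to quit will be offered one box of lozenges" (72 lozenges, no patch). Daily smokers planning to quit are offered patch plus lozenge.
- Patch strength: "Smokers who smoke ≥ 10 cigarettes per day will be offered 21 mg patches"; lighter smokers are offered 14 mg.
- Lozenge strength: "Daily smokers who smoke within 30 minutes of awakening will be also offered the 4 mg lozenges"; the others are offered 2 mg.
- Tolerance: "Daily smokers with a prior reaction to adhesives from bandaids or the nicotine patch will be offered lozenges only".

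On randomisation, Section IV.c says: "We will stratify by practice and readiness to quit in the next 30 days". Patch and lozenge strength are not strata. The Sample size section gives power for days of NRT only (9 v 12 days, 80%) and none for total mg.

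**The concern.** Total mg adds patch mg and lozenge mg, so it reflects two things: how much of the offer a participant used, and how large the offer was. The second is settled by baseline facts and has nothing to do with the text messages. If the regression leaves it out, that variation stays in the residual and widens the confidence interval for the arm difference.

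Readiness is also a randomisation stratum. When a stratum predicts the outcome and is left out of the model, the reported standard error is too large for the design that was used. At stake is the precision of the mg estimate that a later trial would build on.

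**Working it through.** **Supply implied by Section V.b**
- Ready to quit, 14 days of patches: 14 × 21 = 294 mg or 14 × 14 = 196 mg, before any lozenge.
- Not ready, one full box: 72 × 4 = 288 mg or 72 × 2 = 144 mg.
- Seven days of 21 mg patches is 7 × 21 = 147 mg, more than a fully used 2 mg box (144 mg). Total mg therefore does not rank adherence across supply groups.

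**The plan's own power figure.** The 80% for 9 v 12 days cannot be reproduced directly, because no SD is given. With 50 × 0.75 = 37.5 analysed per arm and two-sided alpha 0.05 (alpha is stated for Hypotheses 4 and 5; two-sided is assumed), the implied SD is 3 / [(1.960 + 0.842) × √(2/37.5)] = 3 / (2.802 × 0.2309) = 4.64 days. That SD is used below.

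**Base case for total mg.** From the documents: 68% ready (the feasibility pilot, Section I.b), 9 v 12 days, 37.5 per arm. Assumed: 70% of patch users on 21 mg, 60% on 4 mg lozenges, 10% of ready smokers on lozenges only, 4 lozenges per day of use on average with between-person variation, and days between 0 and 14. Days were multiplied by daily mg under the Section V.b rules, with 400,000 simulated participants per arm.
- NRT arm: mean 217 mg, SD 168 mg. Supply category explains 32% of the variance; readiness alone explains 20%.
- Both arms: difference 70 mg, SD 181 mg. Unadjusted SE = 181 × √(2/37.5) = 41.8 mg; 70/41.8 = 1.67; power = Φ(1.67 − 1.96) = 39%.
- Adjusted for supply category: SE ratio 0.78, so SE = 32.6 mg; 70/32.6 = 2.15; power = Φ(2.15 − 1.96) = 57%.
- Adjusted for readiness only: power 48%.
- The same 3-day effect has 79% power on days.

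A separate simulation of the same comparison gave an SE 19% to 22% lower and power of 38% and 56%.

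**Sensitivity** (base case except as stated)

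| Assumption | SE reduction | Power unadjusted | Power adjusted |
|---|---|---|---|
| Base, 68% ready | 22% | 39% | 57% |
| 2 lozenges/day | 29% | 35% | 60% |
| 8 lozenges/day if ready, 5 if not | 21% | 33% | 48% |
| Not-ready smokers use about 4 days | 28% | 31% | 54% |
| 50% ready | 25% | 33% | 53% |
| 20% ready | 25% | 27% | 44% |
| SD 3 days, 2 lozenges/day | 42% | 46% | 89% |
| All ready | 10% | 56% | 65% |
| All ready, 2 lozenges/day, none lozenge-only | 5% | 70% | 74% |

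The separate simulation put the all-ready reduction at about 4%. The way days are bounded also matters. Normal draws with SD 5 cut off at 0 and 14 turn 9 v 12 into about 8.7 v 10.9, a 2.2-day difference, and power is then 26% unadjusted and 43% adjusted. Those two figures are not the power for a true 9 v 12 difference.

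**The case against.** **The plan is silent on covariates; it does not rule them out.** True, and this comparison is assigned to linear regression outright. But the only adjustment rule stated nearby is triggered by imbalance. That is the wrong trigger for a covariate wanted for precision, and it leaves the choice until data are seen.

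**Readiness is already handled in part.** It is a stratum, and Section VI plans an analysis of treatment use by readiness. This partly stands: readiness supplies much of the gain (39% to 48% of the rise to 57%). But the treatment-use phrase may mean only use of at least one evidence-based treatment. It does not name total mg, and nothing covers strength.

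**Total dose is a deliberate measure.** Section I.a separates execution (total dose) from persistence (duration), and the days outcome does not depend on strength. This stands: differences in mg between products are not pure noise.

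**A stronger reading is tempting: that assigned supply swamps adherence, or distorts the arm comparison.** The documents support neither. Supply explains about a third of the variance in the base case, and more than half only when the SD of days is set low (62% at SD 3). Both arms follow the same baseline rules, so randomisation protects the comparison.

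**The consequence is small.** This stands. The outcome is part (b) of a secondary hypothesis in a pilot, the Sample size section restates Hypothesis 2 with days alone, and base-case power stays below 60% even after adjustment.

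**Conclusion.** The point holds as a loss of precision, not as a bias. With a 68% ready mix, adjusting for baseline supply lowers the standard error for total mg by about 20%; an SE ratio of 0.78 is worth 1/0.78² ≈ 1.6 times the sample. Illustrative power rises from about 38% to about 56% for a true 9 v 12 day difference with SD 4.64. Across the mixed-readiness scenarios examined, the reduction is 21% to 42%; if all participants are ready to quit it is about 4% to 10%.

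All mg figures rest on assumed lozenge counts, strength mix and SD. The 68% comes from a pilot that recruited by letter and a single text, and the trial's mix may differ. This is a free improvement of low priority.

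**What to change.** Add to Section VI, Data analysis: the total-mg regression will include, regardless of observed imbalance, covariates for baseline-determined supply, namely
- readiness to quit and, among ready smokers, eligibility for patch plus lozenge or lozenge only;
- patch strength, coded only within the patch-eligible group, because it is undefined for the others;
- lozenge strength.

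The total-days regression should include readiness.

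Define every term from baseline eligibility, not from the product accepted after randomisation. The documents differ on timing: Section IV.b places the baseline survey before randomisation, while Section IV.c has randomised participants completing it. The sentence should therefore specify values recorded before randomisation, and the two sections should be reconciled.

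The cost is one sentence and four terms, which takes residual degrees of freedom from 75 − 2 = 73 to 69. Cigarettes per day, time to first cigarette and readiness are already in the baseline assessment, and patch and adhesive tolerance is already needed to decide what is offered.
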